10.4 SCHEDULE OF ASSESSMENTS FOR SUBJECTS AGED 1 MONTH - < 2 YEARS

	SCREENING	PRE-ASSIGNMENT		TRE	ATMEN	IT	FOLLOW-UP	
Duration	Up to 21 days	Up to 28 days from Screening	12 WEEKS (equivalent of 84 days)		10-14 days			
Day			1	7-10	28	56	84	94-98
Visit ⁹	1	Pre-assigned ⁶	2	3 ³	4	5	6	7 ^{8,9}
Informed Consent	х							
Eligibility ^{1,7}	х	x	х					
Demographics	х							
Medical History	х							
Physical Examination	х						х	
Vital Signs ²	х	x	х	х	х	х	х	
Clinical Laboratory tests ⁴	х						х	
Haematology, Iron markers ⁵	х		X ¹⁰				х	
PK assessment: Blood Sampling for iron markers, maltol and maltol glucuronide ⁶				X ₆				
PK assessment: Urine sampling for maltol/maltol glucuronide ⁶		X _e		X ⁶				
Treatment Assignment ⁷			х					
Dispense Study Drug		x	х	х	Х	х		
Return Study Drug for Accountability				х	х	х	х	
Adverse Events		х	х	х	х	х	х	х
Concomitant Medications and Procedures	х	х	х	х	х	х	х	х
Compliance reminder			х	х	х	х	х	
Compliance assessment				х	Х	х	х	

CONFIDENTIAL Page 58 of 80

- 1. A subject may be retested once for laboratory criteria that do not meet protocol criteria so long as pre-assignment visit occurs no more than 28 days from the initial screening visit date (if eligible).
- 2. Vital Signs body weight, length, systolic/diastolic blood pressure, pulse, and body temperature at each visit. Patient weight should be recorded at each clinic visit and drug dosing administered as per last clinic visit weight.
- 3. Visit 3 (PK Day 2) this visit will be the second PK day following the pre-assignment PK assessment.
- 4. Clinical Laboratory tests: including
 - a. Clinical Chemistry: Vitamin B12, folate, ALT, AST, alkaline phosphatase, gamma-glutamyl transpeptidase (GGT), total bilirubin, creatinine, amylase, blood urea nitrogen (BUN), phosphorous, sodium, potassium, chloride, calcium, total cholesterol, uric acid, qlucose, total protein, albumin
- 5. Haematology and Iron markers:
 - a. Haematology: Red blood cell count, haemoglobin, haematocrit, mean cell volume (MCV), white blood cell count (total and differential (% and absolute), absolute reticulocyte count and platelet count.
 - b. Iron Markers: serum iron, transferrin, transferrin saturation (TSAT), total and unsaturated iron binding capacity (TIBC, UIBC) and ferritin.
- 6. Pre-assignment phase: All subjects in 1 m-< 2 yrs age group will enter a 1-day PK assessment day prior to entering the treatment phase. Pre-assignment PK Day, each subject has baseline PK urine samples collected immediately prior to ferric maltol dosing (0 h). Following this, subjects will take a single dose of 0.1 ml/kg ferric maltol under supervision. Three (3) PK urine samples will be taken between 0.5 hr -3 hrs, 3 hrs -6 hrs, and 7 hrs -12 hrs post dose. N.B: samples should be taken at least 1.0 h apart. Urine collections instructions are detailed in the study's Laboratory Manual.

PK Day 2 (Visit 3), each subject has baseline PK blood and urine samples collected immediately prior to ferric maltol dosing (0 h). Following this, subjects will take a single dose of 0.1 ml/kg ferric maltol under supervision. Three PK Post-dose blood samples will be collected at the following windows 1.0-2.0 hrs, 3.0-4.0 hrs and 10.0-12.0 hrs; post-dose urine samples will be taken between 0.5 hr -3 hrs, 3 hrs -6 hrs and 7 hrs -12hrs post dose.

In the event of an administered dose not being consumed or partially consumed by the patient this will be noted as a missed dose and will not be repeated.

- 7. Eligibility laboratory sampling/assessments must be completed before the subject is assigned to ferric maltol. The PK samples will be analysed and if evidence of metabolism and elimination of maltol is shown, these subjects will enter the ferric maltol treatment phase Visit 2.
- 8. Subjects who have at least one dose of study medication and withdraw early from the study undergo Visit 7 (Day 94-98) assessments (excluding those who have withdrawn consent).
- 9. Visit 7 is conducted by telephone, unless the subject has an ongoing AE that requires physical examination or investigations for assessment/management. Visit 7 will take place 10-14 days after Visit 6 (Week 12) unless subject discontinued treatment early. All withdrawn subjects should undergo Visit 7 within 10-14 days after the last dose of study drug (if the subject agrees in the case of withdrawn consent).
- 10. Visit Windows: Maximum of 28 days between screening and pre-assignment phase. The Subject must visit to complete:
 - a. Visit 3: must be 7-10 days from Visit 2
 - b. Visit 4: +/- 5 days relative to date of Visit 2/first dose administered
 - c. Visits 5 to 6: +/- 5 days relative to date of Visit 2/first dose administered
 - d. Visit 7: 10-14 days after Visit 6 (unless subject discontinued treatment see Note 10
 - 11. Baseline Haematology and Iron markers: to be performed after urine PK assessment and prior to assignment
 - a. Haematology: haemoglobin
 - b. Iron Markers: serum iron, transferrin, transferrin saturation (TSAT), total and unsaturated iron binding capacity (TIBC, UIBC), ferritin

CONFIDENTIAL Page 59 of 80

10.5 DEMOGRAPHICS AND MEDICAL HISTORY

The following will be documented at Screening and updated (if required) prior to randomisation: Date of Birth, race and ethnicity, gender, all current medical conditions, all medical history relevant to iron deficiency anaemia diagnosis regardless of onset, all clinically significant medical history from the past 5 years (age dependant) including all malignancies, sterilisations, hospitalisations and surgeries; the method of contraception for female subjects of childbearing potential, if applicable. Body weight (Kg), height/length (m/cm) should be recorded at each clinic visit and drug dosing administered as per last clinic visit weight.

PHYSICAL EXAMINATION

A brief physical examination is to be conducted to assess safety. The examination should include an assessment of general appearance, skin, head, eyes, ears, nose and throat, cardiovascular, respiratory, abdominal, gastrointestinal, and musculoskeletal systems.

10.6 CONCOMITANT MEDICATIONS AND PROCEDURES

The following will be documented at Screening and updated (if required) prior to randomisation: all current medications at the time of Screening or stopped within 3 months of screening and any medical procedure performed within 3 months prior to Screening.

The following will be documented throughout the study: any medications initiated stopped or dose and/or frequency changes throughout the study. Any medical procedure performed throughout the study.

Medical procedures to be documented are any therapeutic intervention such as surgery/biopsy, physical therapy or diagnostic assessment (e.g. blood gas measurement).

The exact timing and iron content of any concomitant medications taken on any PK days will be recorded in the eCRF.

10.7 VITAL SIGNS

Body temperature (°C), blood pressure, body weight (Kg), height/length (m/cm) and pulse rate will be assessed. Blood pressure and pulse rate should be measured after the subject has been sitting for at least 5 minutes.

10.8 LABORATORY ASSESSMENTS

10.8.1 Haematology and Clinical Chemistry

Routine clinical laboratory safety bloods for haematology and clinical chemistry/iron markers evaluations will be collected at Screening to assess eligibility. Additional testing may be required if any abnormal value is reported and this must be followed until it is resolved (other

CONFIDENTIAL Page 60 of 80

than iron indices and low haemoglobin due to ongoing iron deficiency/anaemia, or abnormal results due to other pre-existing conditions).

All analyses will be conducted by a central laboratory. Procedures for the collection, processing, storing, and transporting of samples to the laboratory will be fully described in the study-specific Laboratory Manual.

Investigators will review, sign and date all lab results upon receipt from the central laboratory. If a value is flagged as outside of the normal range, the Investigator must document the abnormality as 'clinically significant' (CS) or 'non-clinically significant' (NCS). Any lab abnormality assessed as 'CS' must be recorded as an AE if not explained by a pre-existing condition (documented in the medical history).

The signed paper copy of the laboratory report is retained at the investigational site. The electronic data transferred from the central laboratory database to the clinical study database will be considered source data for the derivation of summary data and listings presented in the clinical study report.

10.8.1.1 Haematology test parameters

Red blood cell count, haemoglobin, haematocrit, mean cell volume (MCV), white blood cell count (total and differential (% and absolute), absolute reticulocyte count and platelet count.

10.8.1.2 Clinical Chemistry and Screening Iron Markers test parameters

Clinical Chemistry: Vitamin B12, folate, ALT, AST, alkaline phosphatase, gamma-glutamyl transpeptidase (GGT), total bilirubin, creatinine, amylase, blood urea nitrogen (BUN), phosphorous, sodium, potassium, chloride, calcium, total cholesterol, uric acid, glucose, total protein, albumin

Iron Markers: serum iron, transferrin, transferrin saturation (TSAT), total and unsaturated iron binding capacity (TIBC, UIBC) and ferritin.

10.8.2 Pharmacokinetics

Blood samples for maltol and maltol glucuronide on each PK day

Blood samples will be collected at the required times on the PK assessment days relative to the time of ferric maltol morning dosing: pre-dose then two further times between 0.5-10 hours post-dose in the 2-17 years age group and pre-dose then three further times between 1-12 hours post-dose in the 1 m to less than 2 years age group (see Section 10.3 and section 10.4).

Following collection and mixing, blood samples will be centrifuged, and the resultant plasma samples separated and stored at -20°C at the study site, prior to collection and onward shipping to the central laboratory on dry ice for subsequent assay of maltol and maltol glucuronide plasma concentrations using appropriately validated bioanalytical methods. Full

CONFIDENTIAL Page 61 of 80

details of the required sample collection, processing and handling logistics will be specified in the study specific Laboratory Manual. Samples will be destroyed at the end of the study, once all analyses are complete.

Blood samples for iron markers on each PK day

Blood samples will be collected at the required times on the PK assessment days, relative to the time of ferric maltol dosing: pre-dose then two further times between 0.5-6 hours post-dose in the 2-17 yrs age group. Same times as blood samples for maltol/maltol glucuronide for each individual (see Section 10.3 and section 10.4.).

Following collection and mixing, blood samples will be centrifuged, and the resultant serum samples separated and split into 2 aliquots at each timepoint. Ambient serum samples will be shipped to the central laboratory for subsequent assay of serum iron, transferrin, transferrin saturation (TSAT), total and unsaturated iron binding capacity (TIBC, UIBC. Frozen serum aliquot will be stored at site (-20°C) for later onward shipping on dry ice to the central laboratory. Full details of the required sample collection, processing and handling logistics will be specified in the study specific Laboratory Manual. Samples will be destroyed at the end of the study, once all analyses are complete.

PK blood sample scheduling in the 2-17 yrs age groups:

3 subjects will be assigned to the required post dose PK blood sampling schedule in sequential order at the time of randomisation, based on current subject enrolment across all study sites. The PK sampling schedule is not the same for each patient, the scheme in the table below has been produced to reduce sampling burden.

PK Sample	PK Sample	PK Sample	PK Sample	PK Sample
Schedule	Schedule	Schedule	Schedule	Schedule
PK Day 1 and	Group 1	Group 2	Group 3	Group 4
PK Day 2	(N=3)	(N=3)	(N=3)	(N=3)
Pre-dose (0h)	Х	Х	Х	Х
0.5 – 1 hour	Х	Х		
1 – 2 hours	Х		Х	
2 – 3 hours		Х		Х
3 – 4 hours			Х	
4 – 6 hours				Х

CONFIDENTIAL Page 62 of 80

PK blood sample scheduling in the 1 m - < 2 yrs age groups:

Pre-assignment PK Day, each subject has baseline PK urine samples collected immediately prior to ferric maltol dosing (0 h). Following this, subjects will take a single dose of 0.1 ml/kg ferric maltol under supervision. Three PK urine samples will be taken between 0.5 hr -3 hrs, 3 hrs -6 hrs and 7 hrs -12hrs post dose.

Note: samples should be taken at least 1.0 h apart. The PK samples will be analysed and if evidence of metabolism and elimination of maltol is shown, these subjects will enter the treatment phase and be assigned to the ferric maltol arm.

PK Day 2 (Visit 3), each subject has baseline PK blood and urine samples collected immediately prior to ferric maltol dosing (0 h). Following this, subjects will take a single dose of 0.1 ml/kg ferric maltol under supervision. Three PK Post-dose blood samples will be collected at the following windows 1.0-2.0 hrs, 3.0-4.0 hrs and 10.0-12.0 hrs; post-dose urine samples will be taken between 0.5 hr -3 hrs, 3 hrs -6 hrs and 7 hrs -12hrs post dose.

Urine samples for maltol and maltol glucuronide

Urine samples will only be collected from subjects aged 1 month to less than 2 years.

Full details of the required sample collection, processing and handling logistics will be specified in the study specific Laboratory Manual. Samples will be destroyed at the end of the study, once all analyses are complete.

10.8.3 Urine Pregnancy Test

Females of childbearing potential only. A urine pregnancy test should be conducted at the Screening visit to assess eligibility using the test kits provided by the central laboratory. A repeat urine pregnancy test will be conducted prior to first dosing on Day 1; the result of this test must be negative for dosing with ferric maltol or ferrous sulfate to commence on Day 1. Repeat urine pregnancy testing will also be conducted at Visit 2, Visit 3, Visit 4, Visit 5, Visit 6.

Full details of the required sample collection and processing procedures will be described in the study-specific Laboratory Manual.

10.8.4 Palatability and acceptability scoring

Subjects aged 2 yrs to 17 yrs on Visit 2 and Visit 4 will receive a 5-point Facial Hedonic scale which will be completed immediately after the administration of ferric maltol oral suspension or ferrous sulfate oral liquid. Subjects are free to ask for support in completing the questionnaires from parents/legal guardian and site staff.

Subjects will complete Visit 2 Facial Hedonic Scale on site, immediately after dosing.

CONFIDENTIAL Page 63 of 80

Subjects can complete Visit 4 Facial Hedonic Scale on site or at home after visit on site and dispensation of Visit 4 treatment, immediately after dosing. If subjects require support in completing the questionnaires from site staff, it is recommended the dosing and subsequent questionnaire completion occur on site.

Questionnaires should be completed immediately after dosing, once a day (morning or evening dose).

Hedonic expression will be converted to scores of 1-5 with 1 being the most positive expression and 5 the most negative. The data from the scales will be transformed into numbers for descriptive statistics.

10.8.5 PK Days food intake

On each PK day: the approximate amount of iron content for any food consumed after ferric maltol and before the end of the PK sampling will be recorded in the eCRF.

10.8.6 Overall blood volume

The individual volume of blood collected throughout the study will be:

- Subjects aged 1 m to less than 2 yrs: up to 24ml (including PK days)
- First 12 subjects aged 2 yrs to 17 yrs in the ferric maltol oral suspension group: up to 27 ml (including PK days)
- ferric maltol oral suspension group without PK sampling (2-17 years): 13 ml
- ferrous sulfate oral liquid group: 13 ml

Blood samples on PK days

Subjects aged 2 yrs to 17 yrs; total number of blood samples on each PK day: 3 timepoints, 1 pre-dose and 2 post doses. Total blood volume at each PK timepoint: 4.5 ml.

Subjects aged 1 month to less than 2 yrs: total number of blood samples on PK blood day: 4 timepoints, 1 pre-dose and 3 post doses. The total blood volume at each PK timepoint: 3.2 ml.

CONFIDENTIAL Page 64 of 80

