In the Phase 1 paediatric PK study, children and adolescents aged 10 to 17 years were administered up to the adult dose of 30 mg BID. Given physiological control of intestinal absorption of iron uptake through the hepcidin pathway and considering a total daily dose of 60 mg iron is within the approved dosage regimen for oral ferrous products in older children, iron overload in a 10-day exposure was considered not to be a risk. Furthermore, in children the metabolism of maltol through glucuronidation in the liver was similar to adults. There was not any great individual clinical benefit over 10 days of ferric maltol therapy, although the information gathered was very important in establishing the doses to be studied in this subsequent Phase 3 paediatric efficacy and safety study in IDA subjects.

Doses chosen for this phase 3 study were based on the first Paediatric PK study and a new age-appropriate formulation has been developed. The study population will recruit subjects with iron deficiency anaemia who are otherwise generally well. The study population will include both female and male subjects aged 1 month - 17 years age range.

From the Phase I PK adult study comparing the ferric maltol suspension and ferric maltol capsule under fed and fasted condition, information was gathered that in the fed condition, ferric maltol capsule and suspension had similar PK with respect to serum iron C_{max} and AUC_{last} .

The C_{max} data suggest that there might be a formulation effect in the fasted state in favor of the capsule with respect to serum iron levels but this was not definitively supported by AUC_{last} and AUC_{inf} comparisons, nor was this supported by the maltol and maltol glucuronide PK.

Ferric maltol suspension had similar PK when administered in fasted or fed conditions with respect to Cmax and AUClast. Nevertheless, we advise ferric maltol should be taken at least 30 mins after meal.

PK assessments will take place for the first 12 subjects in age group 2 yrs -17 yrs) and all 1 m - < 2 yrs assigned to ferric maltol to assess the efficacy, the safety and tolerability of ferric maltol.

This study's procedures risks are related to IV cannulation and blood sampling, with fainting, minor bleeding and bruising regarded as the main risks. Total blood loss as a result of phlebotomy will be approximately 33.8 ml in subject group 1 m to less than 2 years and 40 ml in the 2 to 17 yrs age group.

CONFIDENTIAL Page 37 of 80

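### The 27 ml whole-study blood volume for PK subjects aged 2–17 covers the PK draws only; the protocol's own figures give 40 ml, and its two infant totals (24 ml and 33.8 ml) conflict

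*Protocol*

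**What the plan says.** Protocol Section 10.8.6 opens its list with "The individual volume of blood collected throughout the study will be", so the figures under it are whole-study totals. It then gives:

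- for the PK subset aged 2–17, described as the first 12 ferric maltol subjects of that age: "up to 27 ml (including PK days";
- for children of that age on ferric maltol who give no PK samples: "ferric maltol oral suspension group without PK sampling (2-17 years): 13 ml", with the same 13 ml for the ferrous sulfate arm;
- for infants: "Subjects aged 1 m to less than 2 yrs: up to 24ml (including PK days".

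Below the list, the section describes the PK draws. For ages 2–17 there are three timepoints on each PK day, and "Total blood volume at each PK timepoint: 4.5 ml". For infants there are four timepoints on the one day with PK blood, at 3.2 ml each.

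Protocol Section 5.6 puts total loss from phlebotomy at "approximately 33.8 ml in subject group 1 m to less than 2 years and 40 ml in the 2 to 17 yrs age group". It does not limit the 40 ml to children who give PK samples.

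**The concern.** The two sections give different whole-study totals for the same children: 27 ml against 40 ml in ages 2–17, and 24 ml against 33.8 ml in infants. For ages 2–17, Section 10.8.6 also contains the per-draw volumes needed to test its own total, and the total appears to leave no room for the routine samples.

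The subjects are anaemic, some are only months old, and Section 5.6 counts blood sampling among the main procedural risks. The volume is thus an input to the protocol's own risk-benefit statement. A site or ethics committee that relies on the procedural section reads a lower burden than one that relies on Section 5.6. For the PK subset, the protocol's own sampling schedule exceeds the ceiling set in Section 10.8.6.

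**Working it through.** **Ages 2–17, PK subset**

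Inputs:

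- 3 timepoints per PK day at 4.5 ml each (Protocol 10.8.6).
- 2 PK days, Visit 2 and Visit 3 (Protocol 7.1).
- 13 ml for a child without PK sampling (Protocol 10.8.6).
- Routine laboratory, haematology and iron-marker draws at Screening, Visit 4 and Visit 6 (Protocol 10.3). None falls on a PK visit, so PK sampling cannot absorb them.

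Steps:

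1. PK blood: 3 × 4.5 ml × 2 = 27.0 ml. This reproduces the stated 27 ml exactly, but as PK blood alone.
2. Whole study: 27.0 + 13 = 40.0 ml. This reproduces the Section 5.6 figure exactly.
3. Shortfall: 40 − 27 = 13 ml, and 13 / 40 = 32.5%.
4. Reverse check: for 27 ml to be the whole-study total, the six PK draws would have to share 27 − 13 = 14 ml, or 14 / 6 = 2.33 ml each. The section states 4.5 ml.

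Size of the subset: the first 12 ferric maltol subjects in each of two age groups, so 2 × 12 = 24 of the 98 planned (Protocol 7.1; SAP 2.2.4 also gives 24).

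**Infants, 1 month to under 2 years**

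Inputs:

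- 4 timepoints at 3.2 ml on one PK blood day (Protocol 10.8.6). The pre-assignment PK day is urine only (Protocol 10.4 and 10.8.2).
- Non-PK draws at Screening, Visit 2 and Visit 6 (Protocol 10.4). Their volume is not stated.

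Steps:

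1. PK blood: 4 × 3.2 = 12.8 ml.
2. Gap between the two totals: 33.8 − 24 = 9.8 ml, and 9.8 / 33.8 = 29.0%.
3. Non-PK volume implied by each total, with one assumed value for comparison:

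| Non-PK volume | Infant total | How far 24 ml falls short |
|---|---|---|
| 11.2 ml (implied by 24 ml) | 24.0 ml | 0% |
| 13 ml (assumed, as in ages 2–17) | 25.8 ml | 7.0% |
| 21.0 ml (implied by 33.8 ml) | 33.8 ml | 29.0% |

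The arithmetic leaves both totals open. A non-PK volume of 11.2 ml over three draws is close to the 13 ml that older children give over three draws. A volume of 21.0 ml would be about 60% more than the older children give (21.0 / 13 = 1.62). If anything, 33.8 ml is the harder total to rebuild from the current schedule.

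**The case against.** The strongest reply is that this is a labelling matter. The number of draws and the volume per draw are stated separately, so correcting a total changes no sample. Section 5.6, where risk is weighed, already carries the higher figures. The removed consent pages may carry the right ones. The 13 ml for children outside the PK subset is not shown to be wrong.

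All of that stands, and it limits the point to a documentation error. It does not rescue the 27 ml, which is presented as a whole-study ceiling and is used up by PK blood alone.

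A reader might draw three stronger conclusions, none of which the documents support:

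- **That the infant volume is also understated by about a third.** This takes 33.8 ml as correct. No section establishes that, and 24 ml leaves a workable remainder for the routine draws. The shortfall could lie anywhere from 0% to 29%.
- **That the burden is understated for the trial population.** The demonstrated error concerns only the PK subset. For the other children aged 2–17, the error runs the other way: Section 5.6 attaches 40 ml to the whole age group, although Section 10.8.6 gives 13 ml for those without PK sampling.
- **That the error affects the haemoglobin endpoint.** A wrong total alters neither the blood drawn nor any haemoglobin value, so nothing follows for the primary analysis.

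**Conclusion.** For the PK subjects aged 2–17, the error is established from the protocol's own numbers with no outside assumption. The 27 ml is PK blood only, the whole-study volume is 40 ml, and the stated ceiling is 13 ml (32.5%) too low for a planned 24 children.

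For infants, only a contradiction is established: 24 ml against 33.8 ml. The documents cannot settle it, because the infant non-PK volume is missing.

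The point rests on the per-draw volumes and the 13 ml being correct as stated. The exact agreement with the 40 ml in Section 5.6 supports that for ages 2–17. It should be corrected because a stated limit on blood loss in anaemic children is exceeded by the schedule beside it. It has no bearing on design or analysis.

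**What to change.** 1. In Section 10.8.6, restate the total for the PK subset aged 2–17 as 40 ml (27 ml PK plus 13 ml non-PK). Describe the subset as the first 12 ferric maltol subjects in each of the two age groups, since the present wording can be read as 12 in all.
2. In Section 5.6, say that 40 ml applies to PK subjects only and 13 ml to the other children aged 2–17.
3. Rebuild the infant total visit by visit (Screening, Visit 2, Visit 3, Visit 6), showing PK and non-PK volumes separately, and carry the one resulting figure in both sections.
4. Check that the consent and assent wording gives the same volumes.

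The cost is wording in the protocol and, if needed, in the consent documents. No sample, visit or analysis changes.
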